The standard of care HCV re-infection diagnostic strategy used by HIV outpatient clinics is measuring ALT levels every 6-months. If an ALT elevation is documented, HCV RNA testing is performed to diagnose a potential HCV re-infection. If this HCV RNA test is positive, HCV therapy can then be initiated according to the Dutch HCV treatment guideline.

Figure 1 illustrates the timing of the home-based HCV RNA test in the intervention group; The self-test is done every 6 months in between the ALT tests at the outpatient HIV clinic. Furthermore, the self-test is done at the screening visit as well to exclude that patients with an undiagnosed HCV infection are included.

Figure 1.

Defining the time to diagnosis in the intervention and the virtual control group:

Patients diagnosed with an HCV re-infection by the HCV RNA self-test are contacted immediately by the site investigator and invited to visit the outpatient clinic to have their liver enzymes tested and to confirm the HCV diagnosis with a whole blood HCV RNA PCR test. If at that time the ALT level is elevated, we will assume that an HCV RNA test would have been done by the treating physician at the next 6-monthly HIV outpatient clinic visit (in \pm 3 months) and therefore the HCV diagnosis would have been made at that time point.

In patients diagnosed with an HCV re-infection in which the ALT level turns out to be normal, we will assume that the ALT level would *not be elevated* at the next planned HIV outpatient visit (in general \pm 3 months later), but that it *would be elevated* at the consecutive HIV outpatient clinic visit (in general \pm 9 months later) and therefore the HCV diagnosis would have been made at that time point. This conservative approach that assumes an ALT elevation in all patients 9 months after the positive HCV RNA test is needed because we anticipate that all patients will have started HCV therapy within 6 months after diagnosis and this leads to prompt ALT normalization. Therefore, we cannot use the actual measured ALT level 9 months after the positive HCV RNA test.

[figure not shown]

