4. STUDY POPULATION

4.1 Population (base)

Study population:

Only patients that provide written informed consent will be included. They will first have to review the instruction video that explains and shows how the capillary blood collection and separation of plasma should be done. If the patient is still willing to participate after he has seen the instruction video and received all information by the research team, he will receive the self-testing kit with all materials needed to send in 4 plasma samples over a period of 2 years. The patients will be offered HCV RNA self-testing for 2 consecutive years and thus during 400 patient years of follow-up. Recruitment will stop when at least 1 plasma sample is received from 200 patients. Therefore, we estimate that we will need to include 225 to 250 patients to have an evaluable population of at least 200.

We allow HIV+ as well as HIV- MSM to be included as long as they fulfill the in- and exclusion criteria. HIV negative MSM can only be included if they are taking PREP and if HCV RNA testing is not done as the standard of care HCV diagnostic strategy at the PREP clinic but ALT testing is done as an HCV testing policy no more often than 3x/years. Twice yearly testing is the standard of care in HIV+ patients in the Netherlands but the frequency may be higher or lower in HIV uninfected PREP users per local policy (e.g. in Belgium).

The total number of patients that was informed about the study and the number of patients that reviewed the video but who never actually started using the HCV RNA self-test will be used to evaluate the acceptability of HCV RNA self-testing.

For the statistical analysis the following populations are defined:

Modified Intention to treat population (MITT):

All patients who signed the informed consent, received the HCV RNA self-test kit and in which the HCV RNA test at the screening visit was negative.

Per protocol population (PP):

All patients who signed the informed consent, received the HCV RNA self-test kit and in which the HCV RNA test at the screening visit was negative and who collected all 6 monthly plasma samples during the entire follow-up.

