4.3 Exclusion criteria

A potential subject who meets any of the following criteria will be excluded from participation in this study:

- Age < 18
- Patients that are tested by HCV RNA as a standard of care test (e.g. in the context of PREP use) > 1x/year
- Patients that are expected to be tested by ALT at their HIV or PREP clinic <1x/year

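### The virtual-control diagnosis date for self-test-detected re-infections is written for 6-monthly ALT testing, although eligibility admits men on other ALT schedules

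*Combined protocol and SAP*

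**What the plan says.** Section 3 describes the comparator in these terms: "The standard of care HCV re-infection diagnostic strategy used by HIV outpatient clinics is measuring ALT levels every 6-months". For a re-infection found by self-test, the virtual diagnosis date depends on the ALT measured at confirmation.

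- **ALT elevated:** the plan assumes that "an HCV RNA test would have been done by the treating physician at the next 6-monthly HIV outpatient clinic visit", roughly 3 months on.
- **ALT normal:** ALT is taken to be still normal "at the next planned HIV outpatient visit" and raised at the visit after that. The 3- and 9-month figures are given as typical values. The justification that follows then says that the approach "assumes an ALT elevation in all patients 9 months after the positive HCV RNA test".

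The worked example in Section 3 uses clinic visits at 6, 12 and 18 months. Section 2 and the procedures table in Section 8.3 also show ALT twice a year for every participant.

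The eligibility text is wider. Section 4.1 admits HIV-negative PrEP users if "ALT testing is done as an HCV testing policy no more often than 3x/years", and notes that "the frequency may be higher or lower in HIV uninfected PREP users per local policy". Section 4.3 sets only a floor, which covers both clinic types, by excluding "Patients that are expected to be tested by ALT at their HIV or PREP clinic <1x/year". Section 10 refers back to the Section 3 definition and adds no rule for other ALT frequencies.

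**The concern.** The virtual date is the whole control arm. Both times to diagnosis are counted from the same estimated infection date, so that date cancels in the paired difference. What remains is the gap between the positive self-test and the assumed clinic visit. Any error in the assumed visit date therefore enters the primary effect month for month.

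A man with ALT every 4 months who is given 6-monthly dates is credited with too large a gain. A man with yearly ALT is credited with too small a gain. Only about 16 re-infections are planned, and the primary objective asks to what extent self-testing shortens the time to diagnosis, so the size of the reduction matters as well as its sign. Two analysts could also read Section 3 differently and compute different primary results from the same data.

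**Working it through.** **Inputs**

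- Virtual gaps of +3 months (ALT elevated) and +9 months (ALT normal): Section 3.
- Self-tests at months 3, 9, 15 and 21: procedures table, Section 8.3.
- ALT every 6 months: Sections 2, 3 and 8.3. ALT every 4 or 12 months: my assumption of evenly spaced visits from screening, standing for three tests and one test a year.
- Share q with normal ALT: 25%, range 10-40% (Section 1). That figure is for persistently normal values in chronic infection, so its use at confirmation of a re-infection is an assumption.
- Relevant reduction: at least 2 months (Section 10).

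**1. The plan's own figures.** In the worked example, infection is dated at 6 + (9 - 6)/2 = 7.5 months. The actual time is 9 - 7.5 = 1.5. The virtual time is 12 - 7.5 = 4.5 (ALT elevated) or 18 - 7.5 = 10.5 (ALT normal). The paired differences are 4.5 - 1.5 = 3 and 10.5 - 1.5 = 9. In general, with infection I, self-test S and virtual visit V, the difference is (V - I) - (S - I) = V - S.

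The sample size also reproduces: 2 x (1.96 + 0.84)² x (2/2)² = 15.7, rounded up to 16. It does not involve the ALT interval, so this point leaves it unchanged.

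**2. Gap from self-test to clinic ALT, by schedule (months)**

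| ALT schedule | Next visit (ALT elevated) | Next but one (ALT normal) |
|---|---|---|
| Every 6 months | 3, 3, 3, 3; mean 3 | 9, 9, 9, 9; mean 9 |
| Every 4 months | 1, 3, 1, 3; mean 2 | 5, 7, 5, 7; mean 6 |
| Every 12 months | 9, 3, 9, 3; mean 6 | 21, 15, 21, 15; mean 18 |

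**3. Mean gain per self-test-detected case** = (1 - q) x first gap + q x second gap.

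| Schedule | q = 10% | q = 25% | q = 40% |
|---|---|---|---|
| Every 6 months (the rule) | 3.6 | 0.75 x 3 + 0.25 x 9 = 4.5 | 5.4 |
| Every 4 months | 2.4 | 0.75 x 2 + 0.25 x 6 = 3.0 | 3.6 |
| Every 12 months | 7.2 | 0.75 x 6 + 0.25 x 18 = 9.0 | 10.8 |

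At q = 25%, literal use of the rule overstates the gain by 1.5 months (1.2-1.8 over the range of q) for a man tested three times a year. It understates it by 4.5 months (3.6-5.4) for a man tested yearly.

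**4. Trial level.** The share f of cases off the 6-monthly schedule is not given. At q = 25%, the mean on the men's own schedules is (1 - f) x 4.5 + f x 3.0 or (1 - f) x 4.5 + f x 9.0.

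| f | All off-schedule men 3x/year | All off-schedule men 1x/year |
|---|---|---|
| 10% | 4.35 | 4.95 |
| 25% | 4.125 | 5.625 |
| 50% | 3.75 | 6.75 |

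**5. Sensitivity to self-test timing.** Section 3 places the self-test 3 months after each clinic visit. With three visits a year that would need three self-tests, and only two kits a year are supplied, so I used the table's months. If every self-test of a 4-monthly man did fall 3 months after a visit, his gaps would be 4 - 3 = 1 and 8 - 3 = 5. His mean gain would then be 0.75 x 1 + 0.25 x 5 = 2.0. With half of all cases in such men, the overall mean would be 0.5 x 4.5 + 0.5 x 2.0 = 3.25.

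**The case against.** The strongest reply is that Section 3 does not fix the dates. The normal-ALT limb is tied to planned visits, the month figures are only typical, and the example illustrates one HIV-clinic patient. On that reading, a man's own visit dates already govern. This stands in part: the text can be read that way. But the elevated-ALT limb names the 6-monthly visit, and the justification of the normal-ALT limb speaks of 9 months for all patients. The text supports both readings and does not choose between them.

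The affected group may also be small. The limit of three tests a year and the remark on local variation concern HIV-negative PrEP users only. HIV-positive patients in the Netherlands are described as tested twice yearly, and Section 4.4 speaks of 200 HIV-positive men. The yearly floor covers everyone, but nothing says how many men are near it. This stands, and it is why no trial-level bias can be stated.

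The procedures table could mean that the study imposes 6-monthly ALT on all participants. The rule would then fit the visits, but for PrEP users on another local schedule the comparator would no longer be their standard of care.

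A reader might infer three stronger things that the documents do not support:

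- **That every virtual date is wrong.** The rule covers self-test-detected cases only, and it fits men on 6-monthly ALT.
- **That the bias favours self-testing.** It does so for men tested more often and runs the other way for men tested less often. An equal split of the two groups averages (3.0 + 9.0)/2 = 6.0 months, above the 4.5 credited.
- **That the 2-month criterion is at risk.** A single ALT-elevated man on 4-monthly testing can have a gap of 1 month and be credited with 3. But even if all cases were in men tested three times a year, the mean under the table's timing is 3.0 (2.4-3.6).

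**Conclusion.** The point holds as a rule that is incompletely specified and that, if applied as literally written, gives the wrong comparator time for men whom the plan knowingly enrols. Per self-test-detected case, the illustrative error is an overstatement of about 1.5 months with ALT three times a year and an understatement of about 4.5 months with ALT once a year. These sizes rest on evenly spaced visits, self-tests at the table's months, and a normal-ALT share borrowed from chronic infection.

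The effect on the trial result is unknown because the share of such cases is not given. On every schedule examined each paired difference is positive, so the direction of the signed-rank comparison is unlikely to change. A mean below 2 months is also unlikely: it would take the less favourable timing in step 5 together with most cases coming from men tested three times a year. What would change is the reported size of the reduction. The plan should be corrected before analysis, but the point does not undermine the design.

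**What to change.** In Sections 3 and 10, define the virtual diagnosis date as the participant's own next planned clinic ALT date if ALT is elevated at confirmation, or his next-but-one planned date if it is normal. State that the clinic may be an HIV or a PrEP clinic. Derive the dates from his routine testing interval as recorded at screening. Planned dates cannot be recovered reliably later, because a diagnosis changes care and, under Section 8.4, ends study participation. Keep +3/+9 months only for men on 6-monthly ALT. Add a sensitivity analysis limited to those men.

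Reconcile Sections 2, 3, 4.1, 4.3 and the Section 8.3 table on ALT frequency, and on how self-tests are timed for men not seen every 6 months. Which testing frequency applies is for the sponsor to settle; the analysis rule should follow it.

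The cost is one CRF item and a wording change. The gain shown for more frequently tested men will be smaller.

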As previously mentioned, the HCV *re*-infection rate in HIV+MSM is very high due to ongoing risk behavior. In a prospective case-control study, Vanhommerig et al. identified several risk factors for acquiring an HCV infection. These were receptive unprotected anal intercourse, sharing sex toys, unprotected fisting, injecting drugs during sex, sharing straws when snorting drugs, having a lower CD4 cell count and having a recent diagnosis of ulcerative sexually transmitted infection (19). Various studies report on *re*-infections following SVR in HIV+MSM, but the incidence estimates have a considerable range, which could be explained by differences in study populations regarding risk behaviors, harm reduction interventions and background viremic prevalence (15). In a retrospective study in 606 previously HCV infected HIV+MSM from Austria, France, Germany and the UK, a *re*-infection incidence of 7.3/100 person-years was reported (14). In a smaller Dutch study from the pre-DAA era, Lambers et al. found a much higher HCV *re*-infection incidence of 15.2/100 person-years in 56 HIV+MSM in the Netherlands (20). Consequently, it is clear that HIV+MSM with a previously cured HCV infection have an increased risk of acquiring a new HCV infection. At the moment, HIV+MSM with a previously cured HCV infection undergo ALT testing approximately twice a year during their regular HIV outpatient clinic visit. If an ALT elevation is observed an HCV RNA test is performed to exclude or confirm a new HCV infection. However, in acute and chronic HCV infections ALT is not always elevated. ALT levels correlate with the duration of HCV infection, the viral load and the presence of periportal bridging/necrosis and it has been estimated that up to 25% (range 10 to 40%) of patients with chronic hepatitis C infection have persistently normal aminotransferase levels (21). Given these factors, using an HCV RNA as well as increasing the frequency of ALT testing both have the potential to shorten the time to diagnosis of an HCV *re*-infection significantly. If this is indeed the case, a shorter time to diagnosis (and treatment) will also reduce the time that a patient is at risk of transmitting HCV to others. Therefore, it may be one of the additional steps that is needed towards the elimination of HCV.

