2. OBJECTIVES

The main objective of this study is to demonstrate that the use of a HCV RNA self-test will be an effective and feasible way to decrease the time to diagnosis of an HCV *re*-infection. If this is indeed the case, interventions to prevent HCV transmission to sex partners (e.g. counseling, initiation of DAA treatment) can be initiated sooner after an HCV *re*-infection.

For this purpose, patients will be offered to be trained in capillary blood sampling and separation of plasma at home and will send the plasma sample, by regular post mail, to a central lab for HCV RNA testing. The HCV RNA self-test will be done twice yearly on top of the standard of care ALT testing policy that is also done twice a year at the HIV outpatient clinic. Therefore, patients in the study will undergo HCV testing 4 times a year; twice a year with ALT testing during their regular HIV outpatient clinic visit (followed by an HCV RNA test if the ALT turns out to be elevated) and twice a year with the home-based HCV RNA test. This self-test is done in between the HIV outpatient clinic visits (figure 1).

Primary objective

1. Measure if and to what extent HCV RNA self-testing decreases the time from HCV re-infection to diagnosis compared with the current standard of care.

Secondary objectives:

1. Measure the uptake and acceptability of HCV RNA self-testing in MSM cured of an HCV.
2. Measure the incidence of HCV re-infection in MSM in the Netherlands and Belgium in 2018-2019-2020.

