10. STATISTICAL ANALYSIS

For the primary endpoint the time to HCV re-infection diagnosis will be compared between the intervention group ("The self-testing strategy") and the virtual control group ("The standard of care ALT-based strategy"). Descriptive statistics will be used to quantify the difference in time to diagnosis between these groups. The focus of this study is the feasibility of the diagnostics and therefore to show that the amount of reduction in time to diagnose that the test will lead to is sufficient (i.e. at least 2 months, see paragraph 4.4) to be considered clinically relevant. Since the actual time to diagnosis and the virtual time to diagnosis are measured and estimated for the same patient, these data are dependent. Consequently, for inferential statistics, the Wilcoxon signed rank test will be used in which the virtual time to diagnosis is considered the pre-intervention measurement and the actual time to diagnosis as observed with the self-test intervention will be considered the post-intervention measurement.

The time to diagnosis is defined as the number of days between the calculated time of transmission and the first positive HCV RNA test.

The calculated time of transmission is defined as the midpoint between the date of the last negative and first positive HCV test. For this purpose, the last negative HCV test can consist of a normal ALT level or a negative HCV RNA test.

The analysis of the primary endpoint will be done according to the intention to treat approach and will therefore include the MITT population as described above.

We refer to p.17 for a detailed explanation on how to define the date of the first positive HCV test in the virtual control group.

The analysis of secondary endpoint 1 is similar to the methodology described for the primary endpoint. For the secondary endpoints 2 to 4 descriptive statistics will be used and 95% confidence intervals will be reported.

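### The virtual-control rule dates standard-care diagnosis from ALT alone, although men with one routine HCV RNA test a year may enrol; any such man with normal ALT can be credited with 9 months' gain instead of 3

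*Combined protocol and SAP*

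**What the plan says.** The primary objective (section 2) is to measure whether and how far self-testing "decreases the time from HCV re-infection to diagnosis compared with the current standard of care". The same section describes that standard as twice-yearly ALT with RNA after a raised value, and says that "patients in the study will undergo HCV testing 4 times a year": two clinic ALT tests and two home RNA tests.

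There is no concurrent control. Under section 3, each man found by self-test has his ALT measured, and a virtual standard-care diagnosis date is derived from it. If ALT is raised, the date is the next clinic visit, about 3 months later. "In patients diagnosed with an HCV re-infection in which the ALT level turns out to be normal", the date is the visit after that, about 9 months later. The protocol describes this as "This conservative approach that assumes an ALT elevation in all patients 9 months after the positive HCV RNA test", and explains that later ALT values cannot be used because treatment will have normalised them.

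On routine RNA testing, section 4.3 excludes "Patients that are tested by HCV RNA as a standard of care test (e.g. in the context of PREP use) > 1x/year", so a man with exactly one such test a year is eligible. Section 4.1 admits HIV-negative men only if "HCV RNA testing is not done as the standard of care HCV diagnostic strategy at the PREP clinic". It sets no matching limit for HIV-positive men.

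Section 10 labels the comparator "The standard of care ALT-based strategy", treats a reduction of at least 2 months as clinically relevant, and tests the paired times with the Wilcoxon signed-rank test.

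**The concern.** The eligibility criteria and the control rule do not match. A man with a yearly routine RNA test has a second route to diagnosis under standard care, one that works whatever his ALT. Nothing in section 3, section 10 or Table 12 (section 8.3) takes account of it. If he is found by self-test with normal ALT and his yearly RNA is due at the next visit, the rule passes over a visit at which his clinic would have detected the infection. Assuming raised ALT by 9 months limits the credited gain when ALT is the only route. For this man it enlarges the gain.

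At stake is the estimated size of the reduction, which section 2 asks for and section 10 judges against 2 months. With about 16 re-infections expected, one misdated man is visible in the mean.

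**Working it through.** **The plan's own figures.** In the section 3 example, the last negative test is at month 6 and the self-test is positive at month 9.

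- Estimated infection: 6 + (9 − 6)/2 = 7.5 months. Actual time to diagnosis: 9 − 7.5 = 1.5.
- Virtual time with raised ALT: 12 − 7.5 = 4.5. With normal ALT: 18 − 7.5 = 10.5. Both agree with the protocol.
- Expected re-infections (section 4.4): 200 × 8% = 16. A two-sample calculation (difference 60 days, SD 60 days, two-sided 5%, 80% power) also returns 16 per arm.

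**One man.** The gain is the virtual time minus the actual time.

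- Normal ALT under the rule: 10.5 − 1.5 = 9 months.
- Same man, yearly RNA due at month 12: 4.5 − 1.5 = 3 months. Over-credit: 6 months, or 6/16 = 0.375 month on the mean of 16.
- If his RNA is due at month 18 instead, the gain is 9 either way and nothing is wrong.

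**The mean.** Let q be the share of re-infected men with normal ALT and r the share with a yearly RNA test. The documents do not give r. For q, section 1 offers "up to 25% (range 10 to 40%) of patients with chronic hepatitis C infection have persistently normal aminotransferase levels"; applying this to recent re-infection is an assumption. Also assumed: infections uniform over the year, all self-tests returned, and men first found at a clinic visit counted as zero gain. Take clinic visits at months 0, 6 and 12, yearly RNA at 0 and 12, and self-tests at 3 and 9. Gains by 3-month window of infection are:

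| Group | Rule | Corrected |
|---|---|---|
| Raised ALT | 3, 0, 3, 0 (mean 1.5) | same |
| Normal ALT, yearly RNA | 9, 9, 9, 0 (mean 6.75) | 9, 3, 3, 0 (mean 3.75) |
| Normal ALT, no yearly RNA | 9 throughout | same |

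Credited mean = 1.5(1 − q) + q[6.75r + 9(1 − r)]. Corrected mean = 1.5(1 − q) + q[3.75r + 9(1 − r)]. Over-credit = 3qr.

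| r | Over-credit at q = 25% (q = 10% to 40%), months | Credited / corrected mean at q = 25% |
|---|---|---|
| 0 | 0 | 3.38 / 3.38 |
| 10% | 0.08 (0.03 to 0.12) | 3.32 / 3.24 |
| 25% | 0.19 (0.08 to 0.30) | 3.23 / 3.05 |
| 50% | 0.38 (0.15 to 0.60) | 3.09 / 2.72 |
| 100% | 0.75 (0.30 to 1.20) | 2.81 / 2.06 |

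Half of the normal-ALT men on yearly RNA are misdated, so the expected number in 16 is 8qr. At q = r = 25% that is 0.5, and the chance of at least one is 1 − (1 − 0.5qr)^16 = 40% (18% at r = 10%, 64% at r = 50%).

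**The 2-month mark.** With all self-tests returned, the corrected mean falls below 2 only at q = 10%, where 2.25 − 0.525r < 2 requires r > 0.476. In a simulation of 400,000 infections with 70% of self-tests returned, the mean moves from above 2 to below it when r exceeds about two-thirds at q = 25%, or about 90% at q = 40%. At q = 10% it is below 2 with or without the correction. Among self-test-found men alone, every gain is at least 3, so their mean cannot fall below 3.

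**Test and median.** Every self-test-found man has a positive difference before and after correction. With 10 non-zero differences, the exact two-sided p is 2/2^10 = 0.002 both ways. The median over all re-infections was the same under rule and correction in every scenario run. A median restricted to self-test-found men can move: at q = 40%, corrected gains of 9 have weight 0.40 − 0.30r and gains of 3 have weight 0.30 + 0.20r, so it drops from 9 to 3 once r exceeds 0.2. It still stays above 2.

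**The case against.** The strongest reply is that the affected group is not shown to exist. For HIV-positive men, sections 1, 2 and 3 describe only ALT testing, with RNA after a raised value. The one example of routine RNA in section 4.3 is PrEP use, and section 4.1 largely closes that route. A ceiling on tolerated testing is not evidence that yearly RNA is practised. This stands: r is unknown and may be zero.

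The plan also consistently names an ALT-based comparator, so measuring against each man's own clinic schedule could be called a different choice of control. This stands in part. The objective is nevertheless framed against current standard of care, and for a man with yearly RNA that is not ALT alone.

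A third reply is that the fix may not reduce net bias. If normal-ALT men without yearly RNA would really be found at 15 months rather than 9 (an assumption), the rule under-credits them by 6q(1 − r). This exceeds 3qr whenever r is below two-thirds, and correcting only the over-credit would then move the overall mean further from the truth. This also stands, and it means the direction across the cohort is unknown. It is a reason to state the limits of the 9-month assumption. It is not a reason to keep a wrong date where the right one can be recorded.

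A reader might infer that the control is rigged in favour of self-testing overall, or that a significant result would be an artefact of the rule. The documents support neither: the over-credit is confined to men who may not be present, and the signed-rank result does not depend on it.

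**Conclusion.** The point holds as a narrow, conditional bias in the estimated size of the gain. The rule gives a wrong virtual date for a man the criteria admit: normal ALT at a positive self-test, with a yearly RNA test due at the next visit. He is over-credited by 6 months, which is 0.375 month on the mean of 16. That figure does not depend on r. The effect on the mean does: 3qr, or about 0.19 month if a quarter have yearly RNA and a quarter have normal ALT, and zero if no such men enrol.

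It would be tempting to conclude that the 2-month criterion is in doubt. The crossings found require low normal-ALT prevalence or incomplete self-testing together with a large share on yearly RNA. They also require clinic-found men to be averaged in at zero gain, which the protocol does not state, and the mean to be the deciding summary, which section 10 does not specify. The fix is a cheap improvement; the design does not depend on it.

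**What to change.** - At screening, record whether a standard-care HCV RNA test is scheduled, its interval and when it is next due. Recording it in advance avoids judgement after a positive result.
- In sections 3 and 10, set the virtual diagnosis date at the earlier of the ALT-rule visit and the next scheduled standard-care RNA test after the positive self-test. Keep the 9-month rule for all other men, and state that it may under-credit them.
- Report the number of re-infected men on yearly RNA, and the gain with and without them.
- For clarity, state that a man first diagnosed at a clinic visit has equal virtual and actual times, and show routine and ALT-triggered RNA tests in Table 12.

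The cost is one CRF field, since sites already need the RNA frequency to apply section 4.3, and a few sentences of text. No extra patients or tests are needed. The downside is a possibly slightly smaller credited gain: none if no such men enrol, about 0.19 month at r = 25% and q = 25%.
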